It is anticipated that approximately 1200 patients will be enrolled into this study over an approximately 3.5-year period. Enrollment will continue only until such time as vismodegib becomes commercially available for this patient population. Once the enrollment of 1200 patients is completed, an assessment of how many of patients with metastatic BCC were enrolled under Protocol Amendment Version 4 (dated 8 May 2013) will be made. At that time, enrollment may be extended for up to 15 additional metastatic BCC patients in order to ensure adequate collection of data regarding the effect of vismodegib in metastatic BCC patients, as per Protocol Amendment Version 4 (dated 8 May 2013).

The trial will consist of a Screening Period (Day-28 to -1), a Treatment Phase, an End of Treatment Visit when the patient received the last dose of vismodegib and thereafter discontinues vismodegib (regardless of when it occurs), and five Safety Follow-Up Visits 1 month, 3 months, 6 months, 9 months, and 12 months after the last dose of vismodegib (\pm 5 days), as provided by this phase II safety study protocol. Day 1 of the study will be defined as the first day a patient receives vismodegib.

Enrolled patients will receive study drug until Investigator-assessed disease progression, unacceptable toxicities most probably attributable to vismodegib, patient consent withdrawal, death, reasons deemed by the treating physician, or study termination by the Sponsor.

Patients who discontinue study drug(s) for any reason other than disease progression or withdrawal of consent (e.g., an adverse event [AE]) will continue to be followed until the development of disease progression, consent withdrawal, loss to follow up, or beginning of another anti-cancer therapy.

END OF STUDY

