 - In metastatic BCC patients who develop tumor progression on vismodegib treatment, a biopsy will be performed if at least one of the progressing lesions is accessible, e.g., skin, superficial mass, or lymph node
 - Collection of whole blood in metastatic BCC patients with tumor biopsy at progression

Safety Follow-Up Phase Assessments:

Patients who discontinue vismodegib treatment will be asked to return to the clinic for a safety follow-up assessment 1 month, 3 months, 6 months, 9 months, and 12 months after the last dose of vismodegib (± 5 days), as provided by this phase II, safety study protocol.

- Hematology (including hemoglobin, hematocrit, red blood cell count, full white blood cell count including differential, platelet count, and ANC) as clinically indicated
- Biochemistry (including glucose, sodium, potassium, chloride, bicarbonate, BUN, creatinine, creatine kinase [also known as creatine phosphokinase], total bilirubin, alkaline phosphatase, AST, and ALT) as clinically indicated
- Follow up for disease progression
- Concomitant therapy and new anti-cancer therapy
- AEs (including SAEs)
- For women of childbearing potential:
 - Record date of last menses
 - Assess amenorrhea/irregular menses that develops while on study:
 1. At start of amenorrhea/irregular menses, perform serum hormone evaluation at study site, including FSH, LH, E2, and TSH, and refer to gynecologist or appropriate specialist for assessment of ovaries and uterus, including ultrasound
 2. At resolution of amenorrhea/irregular menses, perform serum hormone evaluation at site, including FSH, LH, E2, and TSH. Refer to gynecologist or appropriate specialist for follow-up ultrasound ONLY if there was abnormality identified during previous ultrasound
 3. If amenorrhea/irregular menses recurs, repeat evaluations at start of recurrence as detailed previously
- Patients with metastatic BCC (newly enrolled after approval of the Study Protocol, version 4.0) will complete the M.D. Anderson Symptom Inventory (see Main Protocol Section 5.6 and Appendix 6), prior to having any other assessments performed at the visits

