4.5 CRITERIA FOR PREMATURE STUDY WITHDRAWAL

Patients have the right to withdraw from the study at any time for any reason.

In the case that the patient decides to prematurely discontinue study treatment (“refuses treatment”), he/she should be asked if he/she can still be contacted for further information. The outcome of that discussion should be documented in both the medical records and in the eCRF. If lost to follow-up, the Investigator should contact the patient or a responsible relative by telephone followed by registered mail or through a personal visit to establish as completely as possible the reason for the withdrawal. A complete final evaluation at the time of the patient’s withdrawal should be made with an explanation of why the patient is withdrawing from the study.

When applicable, patients should be informed of circumstances under which their participation may be terminated by the Investigator without the patient’s consent. The Investigator may withdraw patients from the study in the event of intercurrent illness, AEs, treatment failure after a prescribed procedure, lack of compliance with the study and/or study procedures (e.g., dosing instructions, study visits), cure, or any reason where it is felt by the Investigator that it is in the best interest of the patient to be terminated from the study. Any administrative or other reasons for withdrawal must be documented and explained to the patient.

If the reason for the removal of a patient from the study is an AE, then the principal specific event will be recorded on the eCRF. The patient should be followed until the AE has resolved, if possible.

An excessive rate of withdrawals can render the study non-interpretable; therefore, unnecessary withdrawal of patients should be avoided. Should a patient decide to withdraw, all efforts will be made to complete and report the observations prior to withdrawal as thoroughly as possible.

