5. SCHEDULE OF ASSESSMENTS AND PROCEDURES

All scheduled study assessments are outlined in [Table 1](#) (Schedule of Assessments).

All Screening/Baseline assessments, as outlined in [Table 1](#), must be performed within 28 days prior to the first administration of vismodegib on Day 1, Cycle 1. Results of tests or examinations performed as standard of care before obtaining informed consent and within the 28 days prior to commencing vismodegib may be used. Tumor assessment by physical examination should be performed within a maximum of 7 days prior to the first dose of study drug (baseline reading). If tumor assessment requires imaging, baseline CT/MRI scans should be performed within a maximum of 28 days prior to the first dose of study drug (on Cycle 1, Day 1). Non-measurable disease should be assessed within 28 days prior to study initiation.

All assessments during the Treatment Phase must be performed within a window ± 3 days, from Cycle 2 onwards of the day indicated on the schedule of assessment, with the exception of tumor assessments. The majority of the patients in this study have locally advanced BCC and in this disease setting measurable tumors are accessible to evaluation by physical examination every 4 to 8 weeks (± 5 days). If assessment requires imaging, CT and/or MRI scans should occur every 8 to 16 weeks (± 5 days) or as per institutional standards.

Eligibility for the study will be determined by the Investigator from the mandatory Screening/Baseline assessments performed during screening and according to the study inclusion/exclusion criteria. First dosing of vismodegib will be determined by the patient's eligibility and the laboratory assessments on Day 1 prior to dosing.

The treatment period will begin on Day 1, and patients will be followed until Investigator-assessed disease progression, unacceptable toxicities most probably attributable to vismodegib, patient consent withdrawal, death, reasons deemed by the treating physician, or study termination by the Sponsor. In addition, five Safety Follow-Up Visits 1 month, 3 months, 6 months, 9 months, and 12 months will occur after the last dose of vismodegib (± 5 days), as provided by this phase II safety study protocol. The first anti-cancer therapy received by the patient after discontinuation of study drug will also be recorded.

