5.3.4 Safety Follow-Up Phase Assessments

Patients who discontinue from the study will be asked to return to the clinic for a safety follow-up assessment 1 month, 3 months, 6 months, 9 months, and 12 months after the last dose of vismodegib (+/- 5 days), as provided by this phase II, safety study protocol,

or upon initiation of new non-permitted anti-cancer therapy. The assessments will include:

- Hematology (including hemoglobin, hematocrit, red blood cell count, full white blood cell count including differential, platelet count, and ANC) as clinically indicated
- Biochemistry (including glucose, sodium, potassium, chloride, bicarbonate, BUN, creatinine, creatine kinase [also known as creatine phosphokinase], total bilirubin, alkaline phosphatase, AST, and ALT) as clinically indicated
- Follow up for disease progression
- Concomitant therapy and new anti-cancer therapy
- AEs (including SAEs)
- For women of childbearing potential:
 - Record date of last menses
 - Assess amenorrhea/irregular menses that develops while on study:
 1. At start of amenorrhea/irregular menses, perform serum hormone evaluation at study site, including FSH, LH, E2, and TSH, and refer to gynecologist or appropriate specialist for assessment of ovaries and uterus, including ultrasound
 2. At resolution of amenorrhea/irregular menses, perform serum hormone evaluation at site, including FSH, LH, E2, and TSH. Refer to gynecologist or appropriate specialist for follow-up ultrasound ONLY if there was abnormality identified during previous ultrasound
 3. If amenorrhea/irregular menses recurs, repeat evaluations at start of recurrence as detailed previously
- Patients with metastatic BCC (newly enrolled after approval of the Study Protocol, version 4.0) will complete the M.D. Anderson Symptom Inventory (see Section 5.6 and Appendix 6), prior to having any other assessments performed at the visits
- In selected sites, patients will have blood draws for adverse event–related PK testing if any adverse events that were reported to be related to vismodegib treatment continue to be present at least 6 months after the last dose of vismodegib. Blood samples for the adverse event-related PK testing will be collected at the 6, 9, and 12 months Safety Follow-Up Visits. Blood samples for all time points will be collected even if the adverse event resolves after the 6 months Safety Follow-Up Visit.

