**Additional Note:**

Summaries of amenorrhea are based upon the sub-population of patients who are at risk of this AE, including women of child-bearing potential or having menses at baseline. The demography CRF page captures whether patients are of child-bearing potential but there is nowhere to indicate whether patients have menses, and so all patients who experienced the AE of interest (Amenorrhea/ Irregular Menses) were also included in the denominator.

Overall summary of AEs:

STREAM Template	Description
AET01	Output ID: t_ae_o_* 

● Analysis Population: Safety

● Column Variables: Disease Status (Locally Advanced, Metastatic)

● Column Totals: Totals of non-missing Disease Status

● Analysis Variables: Total Patients with at least one AE, Total number of events, Total number of deaths, Total number of patients withdrawn from study due to an AE, Total number of patients with at least one: AE with Fatal outcome, Serious AE, Serious AE leading to treatment withdrawal, Serious AE leading to dose modification/interruption, AE leading to treatment withdrawal, AE leading to dose modification/interruption

● Numeric Precision and Formatting of Statistics: Use standard display in the mockup

Number of patients reporting AEs:

STREAM Template	Description
AET02	
Output ID: t_ae_*
 

● Analysis Populations: Safety Output will be repeated for different population combinations - please see the LoPO for details of these combinations

● Column Variables: Disease Status (Locally Advanced, Metastatic)

● Column Totals: Totals of non-missing Disease Status

● Analysis Variables: MedDRA System Organ Class, MedDRA Preferred Term.

● Statistics and Calculation Methods: Use proq freq for events or proc sql for patient counts.

● Numeric Precision and Formatting of Statistics: Use standard display in the mockup

● Optional Subsetting: For each System Organ Class and Preferred Term, include Total number of patients with at least one AE, Overall total number of events

Number of patients reporting AEs by Sub-group:

STREAM Template	Description

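### Section 4.5 lets the Investigator take a patient off study for outcome-linked reasons, and the documents disagree on what is then collected and who counts as having completed follow-up

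*Protocol*

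**What the plan says.** Protocol Section 4.5: "The Investigator may withdraw patients from the study in the event of intercurrent illness, AEs, treatment failure after a prescribed procedure, lack of compliance". The list continues with "cure, or any reason where it is felt by the Investigator that it is in the best interest of the patient to be terminated". Where the reason is an AE, the section adds "The patient should be followed until the AE has resolved, if possible". It also calls for a full final evaluation and warns against unnecessary withdrawals. A patient who refuses treatment is to be asked whether contact may continue; no matching step is given when the Investigator initiates the exit.

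Other passages bear on the same patient:

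- Synopsis, Length of Study: patients who stop drug for a reason other than progression or consent withdrawal, with an AE as the example, "will continue to be followed until the development of disease progression, consent withdrawal, loss to follow up, or beginning of another anti-cancer therapy".
- Section 5, opening text: "patients will be followed until Investigator-assessed disease progression, unacceptable toxicities most probably attributable to vismodegib", and further reasons including the physician's. The five safety visits are then added.
- Synopsis, Safety Follow-Up Phase: "Patients who discontinue vismodegib treatment will be asked to return to the clinic for a safety follow-up assessment".
- Section 5.3.4: "Patients who discontinue from the study will be asked to return to the clinic". The visits run from 1 to 12 months after last dose and include AEs and follow-up for progression.
- Sections 7.1.6 and 7.2.2: related SAEs are reported without time limit, unrelated SAEs to 12 months after last dose.

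The SAP treats leaving the study as distinct from stopping drug. Its disposition table has separate rows for the two, and its overall AE summary counts "Total number of patients withdrawn from study due to an AE".

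**The concern.** Safety is the primary objective, and AEs are to be collected through the 12-month visit. AEs, treatment failure and cure are themselves outcomes, or close to them. If a site reads Section 4.5 as ending participation, later data are missing for reasons related to what is being measured. Late AE and SAE counts would then be incomplete in a selective way. The AE-resolution outputs restricted to patients who completed 12-month follow-up would under-represent patients removed because of an AE. PFS and duration of response are censored at the last tumour assessment, and neither document gives a rule or sensitivity analysis for Investigator withdrawal, so that censoring could be informative.

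**Working it through.** **1. One patient, several rules.** Take a patient withdrawn under Section 4.5 for an AE. That patient has also stopped drug for an AE, so the synopsis rule applies as well.

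| Source | What continues after exit |
|---|---|
| Section 4.5 | The AE that caused the exit, if possible; nothing stated on progression or other AEs |
| Synopsis, Length of Study | Follow-up to progression; Investigator withdrawal is not a listed end |
| Section 5, opening | Following ends at toxicity or physician's reasons, plus five safety visits |
| Synopsis, Safety Follow-Up | Five visits for those who stop drug |
| Section 5.3.4 | Five visits, with AEs and progression, for those who leave the study |
| Sections 7.1.6, 7.2.2 | SAE reporting continues |

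Section 4.5 and the synopsis cannot both be the complete instruction. The two safety-visit passages name different groups, and the SAP treats those groups as different.

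**2. The SAP completer rule.** The SAP Disposition text requires the follow-up period to be finished before a patient counts as a completer. It takes the reason for study discontinuation from the End of Follow-Up page. Programming note 1 of Patient Disposition then counts a patient as a completer if that page is present, and note 2 labels completers by last protocol version consented to. Read literally, a version 3 or later patient withdrawn by the Investigator, with the page filed to record this, is tabulated as having completed 12 months. The 24-week table repeats the rule in its note 2, and the 52-week table repeats the 24-week table.

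**3. What is protected.** SAP General AE Reporting limits AE and SAE summary tables, unless otherwise specified, to events starting within 30 days of last dose. Missing later visits hardly touch these.

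**4. Size.** The plan's precision figure reproduces. The exact Clopper-Pearson interval for 120/1200 is 8.36% to 11.84%, against the stated 8.4% to 11.8%. The distances from 10% are 1.64 and 1.84 points, matching the stated 1.6 to 1.8.

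No Investigator-withdrawal rate is given, so the bias cannot be computed. As an illustration only, let w be the share withdrawn with no later events recorded, q = 10% the late-event risk in the others, and r the risk ratio in those withdrawn. All three are assumptions.

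True risk = (1 − w)q + w·r·q; observed = (1 − w)q; shortfall = w·r·q.

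| w | r = 1 | r = 2 | r = 3 |
|---|---|---|---|
| 2% | 0.2 | 0.4 | 0.6 |
| 5% | 0.5 | 1.0 | 1.5 |
| 10% | 1.0 | 2.0 | 3.0 |
| 20% | 2.0 | 4.0 | 6.0 |

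(percentage points)

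The shortfall reaches 1.64 points when w·r = 1.64/10 = 0.164, that is w = 16.4% at r = 1, or 0.164/3 = 5.5% at r = 3. This is a worst case, since Sections 5.3.4, 7.1.6 and 7.2.2 provide for collection after exit. The planned precision is only a yardstick: it concerns AE incidence in 1200 patients, not a late-event proportion.

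**The case against.** A reader might infer that Section 4.5 makes safety and progression follow-up stop. The documents do not support that. Section 5.3.4, read literally, invites patients who leave the study to all five visits, and the SAE rules in Sections 7.1.6 and 7.2.2 are not cancelled by Section 4.5. This part of the objection stands. Its protection is limited, though: the synopsis has a different group in the parallel sentence, so the wording of 5.3.4 may be a drafting slip.

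The Section 5 sentence most naturally describes the treatment period. It opens there and mirrors the dosing-stop list in Section 6.1. It is the weakest of the conflicts.

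A reader might also infer that a patient withdrawn for an AE cannot enter the 12-month completer set. That is too strong. PV3COMP depends on the 12-month follow-up record, and such a patient may still attend that visit. The separate Potentially Reversible AE population does not exclude Investigator withdrawals at all.

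Sparse progression data after treatment are partly a feature of the schedule. Footnote 15 of Table 1 ends physical-examination tumour assessments at end of treatment for everyone, and rewording Section 4.5 would not restore them.

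A count of affected patients built from assumed rates on the 1215 safety patients would not be reliable either. Patients whose last consent was to version 1 or 2 had only one month of follow-up, and a SAP example table shows 298 of them.

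Finally, Protocol Section 8.2.2 already has study discontinuation summarised and listed. That does not repair the completer rule.

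**Conclusion.** The point holds as a conflict between passages that permits outcome-dependent exit, not as proof that data collection ends. Section 4.5 does not separate stopping drug from leaving the study, the synopsis and Section 5.3.4 assign follow-up differently, and the SAP can count a withdrawn patient as a 12-month completer. The exposed results are late AE and SAE counts, AE reversibility in the completer set, PFS and duration of response; the main treatment-emergent AE tables are largely unaffected. The direction and size of any bias cannot be established from the documents. The illustrative shortfalls rest on assumed withdrawal shares and risk ratios and on no data being recorded after exit. The trial is single-arm and descriptive, so no test or error rate is involved. The correction is cheap enough to be worth making.

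**What to change.** **Protocol.** Reconcile Section 4.5, the opening of Section 5, Section 5.3.4 and the two synopsis passages so that Investigator-initiated withdrawal for the listed reasons does not by itself end data collection. State that the five safety visits already scheduled, and the synopsis follow-up to progression, continue unless consent is withdrawn, the patient dies or is lost to follow-up, or the study ends. Keep the coverage in Section 5.3.4 of patients who leave the study, and extend it to all patients off drug. No rule for stopping drug should be added or changed.

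**SAP.** Correct programming note 1 of Patient Disposition and note 2 of the 24-week table (and so the 52-week table), so that an End of Follow-Up page recording study discontinuation does not count as completion. Tabulate Investigator-initiated study withdrawal by reason, as incomplete follow-up.

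**Cost.** Protocol wording and minor reprogramming, with no new visits. Completion counts may come out slightly lower. The notes in Section 4.2 show that enrolment is complete, so the protocol change helps only patients still on treatment or in follow-up; the SAP change applies to everyone in the final analysis.

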5. SCHEDULE OF ASSESSMENTS AND PROCEDURES

All scheduled study assessments are outlined in [Table 1](#) (Schedule of Assessments).

All Screening/Baseline assessments, as outlined in [Table 1](#), must be performed within 28 days prior to the first administration of vismodegib on Day 1, Cycle 1. Results of tests or examinations performed as standard of care before obtaining informed consent and within the 28 days prior to commencing vismodegib may be used. Tumor assessment by physical examination should be performed within a maximum of 7 days prior to the first dose of study drug (baseline reading). If tumor assessment requires imaging, baseline CT/MRI scans should be performed within a maximum of 28 days prior to the first dose of study drug (on Cycle 1, Day 1). Non-measurable disease should be assessed within 28 days prior to study initiation.

All assessments during the Treatment Phase must be performed within a window ± 3 days, from Cycle 2 onwards of the day indicated on the schedule of assessment, with the exception of tumor assessments. The majority of the patients in this study have locally advanced BCC and in this disease setting measurable tumors are accessible to evaluation by physical examination every 4 to 8 weeks (± 5 days). If assessment requires imaging, CT and/or MRI scans should occur every 8 to 16 weeks (± 5 days) or as per institutional standards.

Eligibility for the study will be determined by the Investigator from the mandatory Screening/Baseline assessments performed during screening and according to the study inclusion/exclusion criteria. First dosing of vismodegib will be determined by the patient's eligibility and the laboratory assessments on Day 1 prior to dosing.

The treatment period will begin on Day 1, and patients will be followed until Investigator-assessed disease progression, unacceptable toxicities most probably attributable to vismodegib, patient consent withdrawal, death, reasons deemed by the treating physician, or study termination by the Sponsor. In addition, five Safety Follow-Up Visits 1 month, 3 months, 6 months, 9 months, and 12 months will occur after the last dose of vismodegib (± 5 days), as provided by this phase II safety study protocol. The first anti-cancer therapy received by the patient after discontinuation of study drug will also be recorded.

